#### **4.6 Reasons for Withdrawal after Randomization**

When patients are firstly approached by research assistants, they are informed that they have the right to withdraw their consent to participate at any stage of the trial without influence on their medical care. Therefore, patients with intended withdrawal after randomization is excluded from the study.

As the decision of lung nodule localization need to be made at more than one day before the scheduled surgery to allow for template production, there is the possibility of premature randomization, which is that the assigned patient might not suitable for lung resection after preoperative assessment. Patient whose scheduled lung resection is cancelled is withdrawn from the analysis.

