### **3.5 Statistical Analysis**

To decide whether the localization accuracy, radiation exposure and complication rate in the two groups are significantly different, three tests are used: 1) independent samples  $t$  tests for continuous variables that were normally distributed; 2)  $X^2$  tests for categorical variables, and 3.) Mann-Whitney U test for continuous variables that were not normally distributed.

Because of the possibility of patients withdraw, intention-to-treatment (ITT) analysis and efficacy analysis are both performed. ITT analysis is conducted for participants who received lung nodule localization and subsequent surgery. Efficacy analysis is only performed for patients who received lung nodule localization according to their assignment. All statistical analyses are two-tailed with a significance level of 0.05.

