## **4 STYDT EBROLLMENT AND WITHDRAW**

### **4.1 Inclusion Criteria**

Patient scheduled lung nodule resection by VATS is assessed for eligibility.

The inclusion criteria are as follows.

- (1) The long-axis diameter of the target lung nodule is less than or equal to 20 mm;
- (2) The inner edge of the target nodule is at least 2 cm away from major pulmonary arteries or veins to allow secure nodule excision;
- (3) patient's surgeon in charge must confirm the necessity of preoperative lung nodule localization.
- (4) Male or female  $\geq 18$  years of age

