### **4.3 Treatment Assignment Procedures**

In order to randomly assign the participants to the two groups, a randomization list with 200 numbers was created using blocked randomization with a block size of 10. The 200 random numbers are each placed in sealed envelopes which are marked with sequential number at the cover.

Patients with scheduled lung resection are evaluated by research assistants. If the above criteria are met and patient's consent to participation has also been acquired, then the patient's information is sent to a person who is not involved with the trial by calling. Then, the accorded envelop is opened to assign the patient to template- or CT-guided localization group.

Because of the intrinsic property of the trial, no masking procedure is performed. After assignment, if the patient is allocated to template-guided lung nodule localization, research assistant needs to download the patients CT data from Picture Archiving and Communication Systems. The planned localization route is marked on CT images by patient's surgeon, then the CT data is emailed to designers for template design and printing. Because it takes about 6-8 hours for template production, all enrolled patents have to give consent to participate at least one day before the scheduled surgery.

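### Withdrawals after an unmasked allocation are excluded without separating refusal of the technique from refusal of data use, so the set called ITT is not all randomized patients and Sections 3.5 and 4.6 conflict

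*Combined protocol and SAP*

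**What the plan says.** Section 4.6 tells patients that "they have the right to withdraw their consent to participate at any stage of the trial without influence on their medical care". It concludes that "patients with intended withdrawal after randomization is excluded from the study". It adds a second removal after randomization: "Patient whose scheduled lung resection is cancelled is withdrawn from the analysis".

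Section 3.5 plans two analyses, ITT and efficacy, and gives possible patient withdrawal as the reason. It then defines the first set: "ITT analysis is conducted for participants who received lung nodule localization and subsequent surgery". The efficacy set is limited to patients localized as assigned.

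Two other sections bear on this. Under Section 4.3, consent comes first and then "the accorded envelop is opened to assign the patient to template- or CT-guided localization group". The same section says: "Because of the intrinsic property of the trial, no masking procedure is performed". It puts template production at about 6 to 8 hours, a step that only one arm has. Under Section 4.1, the patient's "surgeon in charge must confirm the necessity of preoperative lung nodule localization" before entry.

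**The concern.** An ITT analysis is meant to protect the comparison against losses that follow from knowing the arm. Section 3.5 invokes it for withdrawal, and Section 4.6 then removes patients who withdraw. Allocation is open and precedes the procedure, and only one arm is offered a new device. The number and type of patients who leave can therefore differ between arms.

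Section 4.6 uses one rule for two different events: declining the assigned technique, and withdrawing permission to use data. In the second case exclusion may be unavoidable. In the first, a localization and a scan may still exist, and dropping them is a choice.

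At stake is the primary comparison of localizer deviation. Two analysts following the document could build different primary sets, and either set would carry a label that readers take to mean all randomized patients.

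**Working it through.** **1. The two sections side by side**

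| Randomized patient | ITT set, Section 3.5 read alone | Section 4.6 |
|---|---|---|
| Declines assigned method, localized by the other method, operated on | In (not in efficacy set) | Out, if declining counts as withdrawal; the text does not say |
| Withdraws consent to participate, still localized and operated on in usual care | In | Out |
| Withdraws permission to use data | Not addressed | Out |
| Resection cancelled | Out | Out |
| Operated on without localization | Out | Not addressed |

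The first two rows are the conflict. The last two show that the set called ITT is not all randomized patients, whichever section prevails.

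**2. The plan's own figures (Section 3.2)**

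Inputs: margin 5 mm, expected difference 3.5 mm (direction not stated), 70 per arm, 90% power, one-sided alpha 0.05, 100 per arm planned. No standard deviation (SD) is given, so the 70 cannot be reproduced directly. Solving the usual formula backwards, with δ the true template-minus-CT difference:

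SD = (5 − δ) × √(70/2) / (1.645 + 1.282)

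- δ = 3.5: SD = 3.03 mm
- δ = 0: SD = 10.11 mm
- δ = −3.5: SD = 17.18 mm

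The dropout allowance is 1 − 70/100 = 30% per arm. At the implied SD, power is 96.8% with 100 per arm, 93.1% with 80 and 90.0% with 70. Loss of power is therefore not the problem. Selective loss is.

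**3. Illustration of selective loss**

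If a share f of the template arm is removed and those patients would have had a mean deviation g larger than the patients retained, the template mean falls by f × g. Neither f nor g is in the documents. With f = 0.10 and g = 5 mm (both assumed), the shift is 0.10 × 5 = 0.5 mm, or 0.5/5 = 10% of the margin.

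With 100 CT patients, 90 template patients and a true difference equal to the 5 mm margin:

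SE = SD × √(1/100 + 1/90); error = P(Z > 1.645 − 0.5/SE)

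| SD (mm) | SE (mm) | 0.5/SE | Error in place of 5% |
|---|---|---|---|
| 3.03 | 0.440 | 1.136 | 30.5% |
| 10.11 | 1.469 | 0.340 | 9.6% |
| 17.18 | 2.496 | 0.200 | 7.4% |

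At SD 10.11 mm and f = 0.10, g = 2 mm gives 6.6% and g = 10 mm gives 16.7%. If the removed nodules were 5 mm easier, the sign changes: P(Z > 1.645 + 0.340) is about 2.4%, and the bias runs against the template.

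**4. The opposite effect of keeping crossovers**

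If a share c of the template arm is localized under CT guidance but analysed as template, a true difference D shrinks by c × D. At D = 5 mm and c = 0.10 the shift is 0.5 mm toward non-inferiority, the same size as in step 3. Retention alone does not settle the matter.

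**The case against.** The best defence is that Section 4.6 concerns withdrawal of consent to participate, not refusal of a technique by someone who stays in the trial. Section 3.5 appears to cover the latter: its two sets would hardly differ unless the ITT set keeps patients not localized as assigned. Consent also precedes the envelope, so a patient unwilling to have the template can decline before randomization. CT-arm patients can withdraw too, so losses need not fall on one side. And retained crossovers bring a bias of their own.

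Much of this stands. It limits how often the problem should arise and makes its direction unknown. It does not remove the conflict, because Section 4.6 never says which kind of withdrawal it means, and its exclusion rule carries no exception for patients already localized.

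A reader might go further and infer that withdrawn patients still undergo localization, so that a measured deviation is thrown away. The documents do not say so. The surgeon's confirmation of need and the promise of unaffected care make localization likely for some who go on to surgery. However, the deviation comes from a computer-aided reconstruction (Section 6.1), and nothing says that this is done for patients outside the trial.

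A reader might also assign the whole 30% allowance to template refusals. With a 5 mm gap that gives 1.5 mm and, with 70 against 100 patients and SD 10.11 mm, an error of 24.4%. Section 3.2 offers the allowance for unspecified dropouts in each arm, and cancelled resections draw on it as well, so it does not support that reading.

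**Conclusion.** The point holds as a conflict in the definition of the primary analysis set. Section 4.6 excludes all withdrawals after an unmasked allocation. Section 3.5 would keep some of the same patients, and the set it calls ITT omits randomized patients who were not localized or not operated on. Exclusions can therefore depend on the arm.

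The amount of bias cannot be established from the documents. The range of 7.4% to 30.5% for a nominal 5% error is an illustration. It rests on an assumed 10% one-arm loss, an assumed 5 mm difference in difficulty, a true difference at the margin, equal SDs in the arms, and SDs back-solved from 70 per arm. Nothing in the plan links withdrawal to harder nodules, and the bias could run either way. This is worth correcting because the rule itself is wrong and the correction is cheap, not because a large error has been shown.

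**What to change.** In Section 4.6, separate (a) declining the assigned technique while permitting data use from (b) withdrawing permission to use data. Keep (a) in the ITT set under the assigned arm, with the deviation measured at the localization actually performed. Exclude only (b) and patients with no localization, and report both by arm and reason.

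In Section 3.5, use the same definition. Do not call the set full ITT if randomized patients without an outcome are omitted.

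Because retained crossovers dilute a true difference, require the non-inferiority conclusion to hold both in this set and in the as-assigned efficacy analysis that is already planned. The efficacy set is itself open to selective loss, so agreement between the two is a safeguard and not proof. The exclusion counts by arm show how much weight each can bear.

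The cost is amended protocol and consent wording, one data field for the type of withdrawal, and a slightly stricter condition for claiming non-inferiority. Nothing in patient care changes.

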## **5 STUDY INTERVENTION**

All lung nodule localization procedures in both groups are performed under the surveillance of a Brilliance 40 CT scanner (Philips Medical Systems, Netherlands) by the same practitioner. And, the percutaneous transthoracic pulmonary nodule localization is conducted using the hookwire localization system (20 gauge, PAJUNK, Germany).

### **5.1 Control Group**

Patients in the CT-guided group received conventional CT-guided percutaneous lung nodule localization using a hookwire system. After patients were positioned on the examining table of the CT scanner (patient's position was decided based on the location of the target nodule), the initial CT scan was conducted through the area of interest using a slice thickness of 3 mm. The localizer insertion site was determined by the CT gantry laser lights and a metal marker on the skin. The insertion length and angle were measured on CT images, and the localizer was then inserted without penetrating the pleura. Afterwards, repeated CT scans were taken to confirm or redirect the localizer in order to obtain adequate accuracy of nodule localization. Based on previous experience, deviations of  $\leq 2$  cm between the localizer and the center of the target nodule were considered accurate enough to allow for safe nodule localization. After confirmation of accurate localizer placement, the practitioner inserted the localizer into

the lung parenchyma and removed the cannula of hookwire.

## **5.2 Experiment Group**

Patients in the template-guided group underwent template-guided percutaneous lung nodule localization using a hookwire. After template placement and prior to hookwire insertion, an initial CT scan is obtained to pre-evaluate the accuracy of nodule localization. If the deviation is less than 2 cm on the initial CT scan, the hookwire is inserted, and the localizer is deployed. However, if the deviation  $>2$  cm based on the pre-evaluation on the initial CT scan, patients would receive conventional CT-guided localization.

After successful nodule localization, the CT scan is immediately obtained in order to evaluate the incidence and severity of the pneumothorax and hemorrhage in both groups. Afterwards, patients are wheeled back to the unit where they wait for the scheduled surgery. During the waiting period, patients are closely observed by nurses, and any occurrence of dyspnea and hemoptysis are detailly recorded.

## **6. Outcome Evaluation**

The characteristics of nodule localization, including accuracy of nodule localization, procedural length, radiation exposure, and related complications are recorded on site by research assistant. Incidence of

localizer dislodgement and margin distance reported by frozen section analysis are collected during lung resection at the operative room.

## **6.1 Measurement of Localization Accuracy**

The accuracy of nodule localization was defined by the deviation between the localizer and the center of the target nodule on CT images. Because the target nodule and localizer are in the three-dimensional space of a patient's thoracic cage, which may not be seen on the same cut of CT scan, it is difficult to precisely measure the deviation directly on the 2D images of CT scan. In order to accurately measure the deviation, computer-aided design (CAD) software is introduced to precisely measure the deviation.

Firstly, patient's thorax is reconstructed based on CT images upon nodule localization. Then the deviation is mathematically calculated using the CAD software.

## **6.2 Procedural Length**

As the start/end point of lung nodule localization can be arbitrary and discrepancy between different researchers, procedural duration was derived from CT scan parameters, which is calculated as the time length between the initial and final scans.

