## **1.2 Rationale**

The navigational template is created based on patient's CT images. Firstly, the CT data is downloaded from Picture Archiving and Communication Systems (PACS), then imported into the computer-aided design (CAD) software to reconstruct patient's thoracic digital model. According to this digital model, the navigational template was designed to mark the puncture site and angle of the localizer prior to nodule localization. In order to achieve accurate template placement on patient's thorax, several anatomical landmarks were marked on the template to check for template alignment.

With the assistance of navigational template, the practitioner does not need to manually calculate the inserting site and angle according to the two-dimensional image, but insert the localizer according to the guidance of template.

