## **1.3 Potential Risks and Benefits**

### **1.3.1 Potential Risks**

The mechanism of template-guided lung nodule localization is the same as conventional CT-guided localization. Therefore, complications related to percutaneous lung nodule localization such as pain, pulmonary hemorrhage, pneumothorax, hemoptysis and so on, likely occur. Most of these complication is non-significant and do not need special intervention.

For patient assigned to receive templated-guided nodule localization, the most worrying concern is the accuracy of lung nodule localization. Firstly, the previous feasibility trial has confirmed the precision of the navigational template, with 10.0 mm of the median localizer deviation and no occurrence of severe complications in template-guided localization. Secondly, for the sake of safety of participants in this trial, patients would receive CT scan to confirm the accuracy of the template-guided lung nodule localization after template placement but before localizer insertion.

Regarding to the concern of infection, the entire template was sterilized by UV irradiation for 30 minutes and the area adjacent to puncture point was sterilized using iodine. And the metal introducer sheath, through which the localizer was introduced, was sterilized using autoclave sterilizer. And infection of the puncture site was not found in our previous study. Additionally, as the template is made of nylon (PA3200), patients with a history of nylon allergy should not receive template-guided localization.

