### **2.2.2 Secondary outcome**

The secondary outcome includes procedural length, radiation exposure dosage and related complication rate.

In order to facilitate the process of data collection, the procedural length of nodule localization was inferred from CT scanning parameter. The time length of nodule localization is calculated from patients receiving the initial CT scan to patients receiving the last CT scan for complication evaluation. And, the radiation exposure dosage (dose-length-product) is directly collected from monitor screen after the last CT scanning. The complication related to percutaneous lung nodule localization mainly includes pneumothorax, pulmonary hemorrhage and hemoptysis during the time of waiting for surgery. The occurrence of pneumothorax and pulmonary hemorrhage is evaluated by CT scanning immediately after localizer release.

Additionally, localizer dislodgement rate and the margin distance reported on frozen analysis are also compared between patients undergoing CT-guided nodule localization and patients receiving template-guided nodule localization.

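### Procedural length is timed from the initial CT, which comes after template placement in the template arm, so on-patient placement time is left out in that arm only

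*Combined protocol and SAP*

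**What the plan says.** Section 2.2.2 lists procedural length as a secondary outcome and defines it thus: "The time length of nodule localization is calculated from patients receiving the initial CT scan to patients receiving the last CT scan for complication evaluation". Section 6.2 repeats the definition ("procedural duration was derived from CT scan parameters, which is calculated as the time length between the initial and final scans") and gives the reason for using scanner times: "As the start/end point of lung nodule localization can be arbitrary and discrepancy between different researchers".

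The intervention sections place the initial scan at different steps:

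- **Control arm (Section 5.1).** Once the patient is positioned on the table, "the initial CT scan was conducted through the area of interest using a slice thickness of 3 mm". Finding the insertion site, measuring length and angle, and inserting the localizer are all described after that scan.
- **Template arm (Section 5.2).** "After template placement and prior to hookwire insertion, an initial CT scan is obtained to pre-evaluate the accuracy of nodule localization". Section 1.3.1 gives the same order: "patients would receive CT scan to confirm the accuracy of the template-guided lung nodule localization after template placement but before localizer insertion".

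Section 1.2 shows that placement is a task done on the patient: "several anatomical landmarks were marked on the template to check for template alignment".

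Both arms end at the CT taken immediately after localization to look for complications. No section sets a common start, describes a scan before placement in the template arm, or asks for placement time to be recorded.

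**The concern.** The outcome has one definition, but its starting event is not equivalent in the two arms. Placing and aligning the template is on-patient work that falls before the clock starts. A precise scanner time does not help if the first scan marks a different step in each arm.

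The point is limited to that step. The control arm's on-table measurement of angle and length is real procedure time, and a device that removes it has a genuine effect. Offline route marking and template production may reasonably be excluded.

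At stake is how a secondary comparison is read. Making localization easier is one of the device's stated purposes (Sections 1.1 and 1.3.2), so a shorter procedural length would naturally be cited in its support. The distortion is systematic: a larger sample estimates the wrong quantity more precisely.

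**Working it through.** The plan states no figure for procedural length, so there is nothing to reproduce. The check sets the order of steps against the clock definition, then illustrates the consequence.

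**1. Order of steps**

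| Step | Control arm | Template arm |
|---|---|---|
| Positioning | Before the clock | Before the clock (taken to precede placement) |
| Template placement and landmark check | Not applicable | **Before the clock** (5.2, 1.3.1, 1.2) |
| Initial CT | Clock starts (5.1) | Clock starts (5.2) |
| Finding site, measuring angle and length | Timed, as described after the scan (5.1) | Not needed; set by the template (1.2) |
| Insertion, any redirection, release | Timed | Timed |
| Complication-check CT | Clock stops | Clock stops |

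Only the placement row is on-patient work that goes untimed in one arm alone.

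**2. Bias in minutes**

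Let *p* be template placement and alignment time, and *c* any control set-up time between positioning and first scan. The amount by which template-arm time is understated relative to control is *b* = *p* − *c*. The documents give neither, so these values are assumed:

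| *p* (min) | *c* = 0 | *c* = 1 | *c* = 2 |
|---|---|---|---|
| 2 | 2 | 1 | 0 |
| 5 | 5 | 4 | 3 |
| 10 | 10 | 9 | 8 |

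If *p* ≤ *c*, the bias is nil or reversed.

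**3. Effect on the test**

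Inputs from the documents: 100 per arm (Section 3.2) and two-sided 0.05 (Section 3.5). Assumed: a two-sample t test, no true difference in total time, and *b* in SD units. The test statistic is then noncentral t with 2*n* − 2 degrees of freedom and noncentrality (*b*/SD) × √(*n*/2). With *n* = 100, √50 = 7.07, so 0.2 SD gives 0.2 × 7.07 = 1.41.

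| Net bias (SD) | Noncentrality, *n* = 100 | Probability of p < 0.05 |
|---|---|---|
| 0.1 | 0.71 | 0.108 |
| 0.2 | 1.41 | 0.291 |
| 0.3 | 2.12 | 0.560 |
| 0.4 | 2.83 | 0.804 |
| 0.5 | 3.54 | 0.940 |

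The nominal value is 0.05. At 0.2 SD, 400 per arm gives noncentrality 0.2 × √200 = 2.83 and probability 0.806, so more patients make the false finding more likely.

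**4. Linking minutes to SD units**

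Divide the net minutes by the SD, which must also be assumed. With 100 per arm and a normal approximation:

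| Net bias (min) | SD 3 min | SD 5 min | SD 8 min |
|---|---|---|---|
| 1 | 65% | 29% | 14% |
| 2 | 99.7% | 81% | 42% |

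For example, 1 min over an SD of 5 min is 0.2 SD, which agrees with the 29% in step 3.

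**5. Converted patients**

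If the deviation on the template-arm initial scan exceeds 2 cm, "patients would receive conventional CT-guided localization" (Section 5.2). The documents do not say whether the clock keeps running from that scan or restarts. Placement time is left out either way.

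**The case against.** **Scanner times were a reasoned choice.** They avoid disagreement between researchers about when a procedure starts, and neither section calls the interval total procedure time. This stands as a reason for keeping the scanner interval. It addresses reliability of measurement, not whether the first scan marks the same step in both arms.

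**Direction and size are not established.** Section 5.1 mentions a skin marker without saying explicitly whether it went on before or after the initial scan. If before, some control set-up is also untimed. The probabilities are generic t-test results that rest on assumed biases and SDs and on equal true times. All of this stands: the figures show sensitivity and are not evidence about this trial. Section 5.1 describes nothing but positioning before the first scan, so a bias favouring the template remains the expected direction, but not a certain one.

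**Converted patients could pull the other way.** If their clock runs from the first scan, it includes the failed template check, which lengthens template-arm time. This stands, and the plan should say which rule applies.

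**The consequence is limited.** This is one of several secondary outcomes, and the opening sentence of Section 3.5 does not name it among the variables to be tested. That limits the importance of the point. Section 2.2.2 still names it as an outcome, and the comparison would be non-equivalent.

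**A manual start time has its own error**, because unmasked staff would record it. This stands as a cost of the remedy.

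**Conclusion.** The concern holds. Followed as written, Sections 2.2.2 and 6.2 compare intervals that begin at different steps, and template placement and alignment go untimed in the template arm only. This follows from the order of steps in Sections 5.1, 5.2 and 1.3.1 and needs no numerical assumption.

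The net size cannot be computed from the documents. The expected direction favours the template, on the assumption that placement takes longer than any control set-up before the first scan. The probabilities above also assume a t test and no true difference in total time. With skewed times Section 3.5 would lead to a Mann-Whitney test; the figures would then be approximate, but the shift would remain.

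The plan should be changed, but the point is confined to this secondary outcome. The primary comparison of localizer deviation is unaffected.

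**What to change.** In Sections 2.2.2 and 6.2, define one start event for both arms that precedes both template placement and the first scan, for example the patient being positioned for the procedure. Have the research assistants record its time. Keep the complication-check CT as the end. State that template patients converted to CT guidance keep the same start.

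Retain the scanner-derived interval as a supportive measure labelled *scan-to-scan, excludes template placement*. If start times cannot be collected, give the outcome that label and do not present it as total procedure time.

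The cost is one extra recorded time per patient, plus wording in two sections. At least two assistants already attend each localization (Section 6.4.1), and procedural length is already recorded on site (Section 6). The drawback is a manual timestamp by staff who know the allocation (Section 4.3), which brings back some of the observer variation that Section 6.2 set out to avoid. A single, clearly defined event limits this, and the scanner interval remains as a check. Clinical management does not change.
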